### 2.2 Primary and secondary endpoints

Primary Endpoint: Changes in muscle strength in the lower limbs following the 8-week strength training intervention of the lower limbs in three study groups with different training volumes. The two strength-specific primary outcome parameters are: 1RM and H:Q ratio. Changes in 1RM and H:Q ratio will be derived using the *iOS Strength Control app* and biomechanical analysis before and after the strength training intervention. Primary outcome parameters will be compared between the three study groups in relation to training volumes (Group#1: no training, Group#2: 1 training per week, Group#3: 3 trainings per week). The accuracy in the prediction of 1RM and H:Q ratio will be compared with data from isokinetic strength tests as gold standard.

Secondary Endpoint: Changes in muscle size of the lower limbs following the 8-week strength training intervention of the lower limbs in three study groups with different training volumes. The two secondary outcome parameters are: muscle volume and CSA. Changes in muscle volume and CSA will be derived using the HMF technique in combination with data from 3D body surface scanning and anthropometric measurements before and after the strength training intervention. Secondary outcome parameters will be compared between the three study groups in relation to training volumes (Group#1: no training, Group#2: 1 training per week, Group#3: 3 trainings per week). The accuracy in the derivation of muscle volume and CSA using the HMF technique will be assessed using data from MRI and ultrasound as gold standard.

Key baseline factors that will likely influence the primary and secondary endpoints are strength training experience and gender. The sample size and population group are specified to allow the analysis of gender-specific differences on study results. Thereby, the inclusion/exclusion criteria and study protocol, including a training-related questionnaire, are defined to minimize the bias of training experience.

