## 3 PROJECT POPULATION AND STUDY PROCEDURES

### 3.1 Project population, inclusion and exclusion criteria

Project population: The project population are healthy adult subjects who are all participating in their own strength training program on a regular weekly basis. The primary objective is to predict changes in muscle strength (i.e. primary outcome parameters: 1RM and H:Q ratio) following different training volumes of key muscle groups associated with knee joint stability. A power analysis was conducted using statistikguru.de to assess the required sample size for the primary outcome parameter, 1RM. A Cohen's of  $d=1.5$  was assumed based on previously reported changes in absolute and relative strength following an 8-week strength training intervention in 19 professional rugby league players, with reported changes in squat 1RM pre:  $170.6 \pm 21.4$  kg, post:  $200.8 \pm 19.0$  kg,  $p < 0.001$ ; and squat 1RM/(body weight) pre:  $1.78 \pm 0.27$  kg·kg, post:  $2.05 \pm 0.21$  kg·kg,  $p < 0.001$ ; respectively [52]. Given 3 study groups, alpha was set at 0.025. With a

power of 0.9, the required sample size is 11 participants per study group for drawing statistically significant conclusions. Based on the power analysis, we aim for a total of  $n=36$  complete data sets ( $n=12$  per study group of the strength training intervention), with a sub-group of  $n=12$  participants additionally scheduled for MRI of the lower limbs at baseline.

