The MRI-based assessment of muscle volume for validation of the HMF technique is analyzed independently from the strength training intervention. Thereby, the accuracy of the HMF technique is dependent on the initial generic musculoskeletal model that is used for model fitting, as well as the available subject-specific skin surface and anthropometric data. The level of significance in the difference of muscle volume between HMF and MRI is expected to vary across muscle-tendon groups, as well as between population groups and gender. In particular, no significant differences were found in the predicted volume of semitendinosus and semimembranosus as part of the hamstrings between HMF and MRI in 5 children without CP (MRI 5.1 (0.91) versus HMF 5.0 (0.30)  $\text{cm}^3/\text{kg}$ ,  $p\text{-value} > 0.05$ ) and in the predicted volume of the quadriceps, including vastus lateralis, medialis, intermedius and rectus femoris, in 6 children with CP (MRI 15.9 (3.20) versus HMF 16.5 (2.58)  $\text{cm}^3/\text{kg}$ ,  $p\text{-value} > 0.05$ ), respectively [22]. Based on previous research, it can be expected that additional consideration of somatotype from anthropometric measurements will help to improve model fit by allowing to adjust the relative thickness of the skin layer, and thus segmental inertia properties, via the HMF objective function for individual subjects. Furthermore, it is very likely that the accuracy in fitting results will be improved when fitting a generic musculoskeletal model to subjects of similar age and gender, and without significant musculoskeletal impairments, which will be the case in the present study. Further details to the MRI-based analysis are provided in Subsection 3.3.

All participants have to confirm their voluntary participation with a written informed consent before being submitted to any study procedure.

Inclusion criteria (all participants,  $n=36$ ):

- Healthy participants; and
- Age 18-40 years old; and
- No acute or chronic musculoskeletal symptoms or pain; and
- Experience with strength training (at least 1-year strength training experience with one training session per week or more); and
- Familiar with strength exercises of key muscles associated with knee joint stability.

Exclusion criteria (all participants,  $n=36$ ):

- Acute or chronic musculoskeletal pain; and/or
- Musculoskeletal surgery within the last 12 months; and/or
- Ongoing rehabilitation or treatment of musculoskeletal complaints or injury; and/or

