#### PHASE A: Screening, informed consent & baseline measurements.

- **1st Visit:** Screening, informed consent, health- and training-related questionnaire, allocation into three study groups (Group#1: no training, Group#2: 1 training per week, Group#3: 3 trainings per week). The approximate duration of the 1st Visit is **1h**.
- **2nd Visit:** Baseline measurements. 3D body surface scan, anthropometric measurements, ultrasound, isokinetic strength tests, iPhone/watchOS measurements and optical motion capture during exercise execution. The approximate duration of the 2nd Visit is **4h**. The time between the 1st and 2nd visit is defined within two weeks of the 1st visit to fit in with the participant's schedule.
- **MRI scan** (sub-group,  $n=12$ ): An additional visit is scheduled for the sub-group of  $n=12$  participants to obtain data from MRI of the lower limbs. The scan time is 10-15 minutes, with the total duration of the visit to the MRI facilities at the SCMI being approximately **30**

**minutes.** MRI data acquisition is individually defined within two weeks of the 1st visit to fit in with the participant's schedule.

PHASE B: 8-week strength training intervention. Conduct of an 8-week strength training intervention of key muscle-tendon groups associated with knee joint stability in the training-specific setting of each participant. Participants are randomly allocated into three study groups with increasing levels of loading (Group#1: no training, Group#2: 1 training per week, Group#3: 3 trainings per week) with the same number of subjects and gender distribution in each group ( $n=12$  per group, 6F and 6M). The same guidelines for the warm-up and the type of exercises will be given prior to the intervention study to each participant. Participants are asked to record exercise load and volume as well as monitor training-related variables and 1RM using the *iOS Strength Control app*. Participants perform the strength training self-directedly in their chosen fitness/training facilities as it fits into their weekly routine. Contact to the study investigator is ensured at all times in case of questions.

PHASE C: Post-intervention measurements.

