## 4 STATISTICS AND METHODOLOGY

### 4.1. Statistical analysis plan

Statistical analysis will be conducted with SPSS (SPSS v. 21, IBM, USA) after consultation with a statistician in line with previous research by our group.

For the Primary Objective, a repeated measures analysis of variance (ANOVA) will be conducted to assess statistically significant differences between the predicted values of 1RM and H:Q ratio from biomechanical modelling and mobile monitoring with the measured values from optical motion capture and isokinetic strength tests following the 8-week strength training intervention. A correlation analysis will be done to relate the strength-specific outcome parameters to the training-specific parameters for each study group. Principal component and factor analysis will be performed to identify correlations between strength-specific and training-specific parameters.

For validation of the HMF technique, we will follow the statistical methods of previous research by our group [21, 22] to assess the significance in the differences of muscle volume between HMF and MRI, as well as the difference of the predicted adaptation in CSA between HMF and ultrasound. The level of significance in the difference of muscle volume between HMF and MRI is expected to vary across muscle-tendon groups and gender. In particular, no significant differences were found in the predicted volume of semitendinosus and semimembranosus as part of the hamstrings between HMF and MRI in 5 children without CP (MRI 5.1 (0.91) versus HMF 5.0 (0.30) cm^3/kg, p-value >0.05) and in the predicted volume of the quadriceps, including vastus lateralis, medialis, intermedius and rectus femoris, in 6 children with CP (MRI 15.9 (3.20) versus

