HMF 16.5 (2.58) cm^3/kg, p-value > 0.05), respectively [22]. It is expected that the accuracy in the predicted muscle volume is improved in the present study by fitting a generic musculoskeletal model to subjects of similar age and gender, and without significant musculoskeletal impairments, as well as additionally considering subject-specific somatotype based on anthropometric measurements. ANOVA will be performed to analyse the pairwise differences in muscle volumes between the HMF and MRI-based results; and to analyse the pairwise differences in the predicted adaptation of hamstrings and quadriceps CSA between HMF and data from ultrasound before and after strength training intervention, respectively. The data from female and male participants will be analysed combined, as well as independently as two different groups.

The level of significance will be set at  $p < 0.05$  for all statistical tests.

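### Allocation is balanced by sex, but no sex term is named for the three-group comparison; a combined analysis without one loses power to the extent that the outcome differs by sex

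*Combined protocol and SAP*

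**What the plan says.** Sections 2.3 and 3.3 (Phase B) allocate 36 participants at random to three groups of 12, "with the same number of subjects and gender distribution in each group", which means 6 women and 6 men per group. Section 2.2 states: "Key baseline factors that will likely influence the primary and secondary endpoints are strength training experience and gender".

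Section 2.2 also promises a between-group comparison for the primary outcomes: "Primary outcome parameters will be compared between the three study groups in relation to training volumes". It promises the same for muscle volume and CSA. The sample size in section 3.1 rests on 1RM and three groups.

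Section 4.1 specifies two kinds of analysis, both within-person:

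- The strength predictions are set against the measured values: "a repeated measures analysis of variance (ANOVA) will be conducted to assess statistically significant differences between the predicted values of 1RM and H:Q ratio".
- For the imaging outcomes, "ANOVA will be performed to analyse the pairwise differences in muscle volumes between the HMF and MRI-based results", and likewise for CSA against ultrasound.

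The only statement about sex as an analysis factor closes the imaging paragraph: "The data from female and male participants will be analysed combined, as well as independently as two different groups". Section 4.1 names no sex factor, covariate or interaction, and gives no model for comparing the three groups.

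**The concern.** When allocation is exactly balanced on a factor, the true sampling error of a group difference contains only the variance within levels of that factor. An analysis that omits the factor still counts the difference between its levels as residual noise. The estimate is unbiased, but its standard error is too large, its interval too wide and its test conservative. The precision obtained by balancing on sex is then not used.

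At stake is the power of the comparison for which the trial was sized. The separate analyses cannot make up for it. With 6 against 6 in each sex and d=1.5, power is 65% at two-sided 0.05 and 51% at two-sided 0.025. The combined analysis has to carry the inference.

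**Working it through.** **The plan's own figures (section 3.1).** Squat 1RM is 170.6 (SD 21.4) kg before and 200.8 (SD 19.0) kg after. The difference is 30.2 kg, the pooled SD is sqrt((21.4² + 19.0²)/2) = 20.2 kg, and d = 30.2/20.2 = 1.49, which the plan rounds to 1.5. A two-sample t-test with d=1.5 and one-sided alpha 0.025 needs 11 per group (power 91.7%), as stated. With two-sided alpha 0.025 and the planned 12 per group, power is 88.9%.

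**Effect of leaving sex out.** Let g be the difference between the sexes in the analysed outcome, in within-sex SDs, equal in all groups. The documents give no value, so g is varied from 0 to 2. In a group with 6 women and 6 men, the sex difference adds 12 × (g/2)² = 3g² to the within-group sum of squares. For two groups with 22 residual df, the expected residual variance is 1 + 6g²/22 instead of 1. The ratio is the same for three groups (9g²/33). Interval width is inflated by about the square root: at g=1, sqrt(1 + 0.273) = 1.13.

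Simulated power at two-sided alpha 0.025, d=1.5 in within-sex SDs, 12 per group:

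| g | Width ratio | Two-group test, no sex term | Two-group test, sex term | Three-group model, no sex term | Three-group model, sex term |
|---|---|---|---|---|---|
| 0 | 1.00 | 89% | 89% | 90.1% | 90.0% |
| 0.5 | 1.03 | 87% | 89% | 88.7% | 90.0% |
| 1 | 1.13 | 82% | 89% | 84.1% | 90.0% |
| 1.5 | 1.27 | 72–73% | 89% | 74.9% | 90.0% |
| 2 | 1.45 | 58% | 89% | 60.9% | 90.0% |

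In the three-group model without sex, the true type I error at nominal 2.5% falls from 2.4% at g=0 to 1.2% at g=1 and 0.1% at g=2. At alpha 0.05, the level set in section 4.1, power without sex is 94.6%, 93.8%, 91.0%, 85.5% and 76.2% down the same rows, against 94.5% with it.

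**If only the trained group differs by sex.** Take the 30.2 kg effect, treat 20.2 kg as the within-sex SD, and let women and men differ by 10, 20, 30 or 40 kg in the trained group only. At alpha 0.05 a sex main effect gains about 0.1, 0.8, 2.1 and 4.2 points. With the same differences in both groups, power without sex is 92.9%, 89.8%, 84.1% and 74.4% against about 93.7% with it: gains of 0.8, 3.9, 9.6 and 19.3 points.

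**Within-person contrasts.** A difference between two methods in the same person removes any sex difference in level. In an illustrative paired comparison with n=12, power is 71.7% without and 70.8% with a sex term, whatever the sex difference in level. Only a method difference that itself varies by sex changes this: with a sex gap of 1 SD of the paired difference, power is 62.0% without the term and 70.8% with it.

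**The case against.** The strongest objection is about placement. The sentence on combined and separate analysis closes the paragraph on validating host mesh fitting (HMF), whose contrasts are within-person, as is the primary predicted-versus-measured ANOVA. Section 3.1 adds: "The MRI-based assessment of muscle volume for validation of the HMF technique is analyzed independently from the strength training intervention". This stands. The allocation balance does not bear on the MRI subset, and a reader who inferred that every analysis in section 4.1 loses power would be wrong.

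Second, section 4.1 gives no between-group model, so a pooled test without sex is an inference about what will be run. This also stands, and it makes the point conditional. The gap is itself a reason to specify the model now, because the one sentence on sex points to a combined analysis without it.

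Third, the larger losses need large sex differences. The endpoint in section 2.2 is change. A sex share of 25% of the outcome variance implies a difference of 2 × 20.2 × sqrt(0.25/0.75) = 23 kg, or 77% of the assumed 30.2 kg effect, and a common effect imposes it on the no-training group too. If only trained participants differ by sex, the gain is small and a sex main effect captures only part of the difference. The 20.2 kg is also an SD of levels, while the SD of change is not given. This stands against quoting any single figure.

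Two stronger readings are tempting. One is that the trial's inference is invalid; but the omission makes tests conservative and does not inflate type I error. The other is that d=1.5 holds only within one sex, because the SD was taken "based on previously reported changes in absolute and relative strength following an 8-week strength training intervention in 19 professional rugby league players". The plan does not give the sex of that squad, so this remains an assumption.

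Finally, sex is not ignored: by-sex analyses are planned and a statistician will be consulted. With 6 per sex per group, those analyses do not replace a sex term in the combined model.

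**Conclusion.** The point holds in conditional form. Sex is balanced by allocation and declared influential, yet no sex term is named for the three-group comparison. If that comparison is run combined without sex, the cost is efficiency, in proportion to how far the analysed outcome differs by sex. For a common sex difference of 0 to 2 within-sex SDs, power at two-sided alpha 0.025 drops from about 89% to 58% in a two-group test, with 82% and intervals about 13% wider at 1 SD. The loss is only 0.1 to 4.2 points at alpha 0.05 if the trained group alone differs by 10 to 40 kg, and near zero if the sexes do not differ on the analysed outcome.

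These sizes rest on assumed sex differences and on d=1.5 taken as a within-sex effect. The documents do not say where in the range the trial will fall. Predicted versus measured, HMF versus MRI and HMF versus ultrasound are affected only through a sex-by-method or sex-by-time difference.

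**What to change.** In section 4.1, state that each between-group comparison of 1RM, H:Q ratio, muscle volume and CSA is made in one model on all participants, with group and sex (the allocation factor) as fixed effects. State that the separate female and male analyses, with 6 per group, are descriptive.

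Optionally, add a method-by-sex term to the HMF comparisons, since section 4.1 itself expects the significance of the HMF–MRI difference to vary with gender.

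The cost is one factor in the SPSS model, with no new data. It uses one residual degree of freedom, about 0.1 to 0.2 points of power in the between-group comparison if sex has no effect. The optional term can cost slightly more in the MRI subset of 12: 71.7% to 70.8% in the illustration above, if the method difference does not vary by sex.

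### Section 3.1 sizes the trial at alpha 0.025 for three groups, section 4.1 tests everything at 0.05 with no rule for two primary outcomes, and the gender-specific sizing claim has no calculation behind it

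*Combined protocol and SAP*

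**What the plan says.** All references are to the combined protocol and SAP.

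- **Sizing (section 3.1).** The calculation was run "to assess the required sample size for the primary outcome parameter, 1RM". It uses an effect size ("A Cohen's of $d=1.5$ was assumed") and a reduced alpha ("Given 3 study groups, alpha was set at 0.025"), and concludes: "power of 0.9, the required sample size is 11 participants per study group". The plan is 12 per group, 36 in all. Section 3.3 gives 6 women and 6 men in each group.
- **Testing (section 4.1).** "The level of significance will be set at $p < 0.05$ for all statistical tests". No section gives a multiplicity procedure, an order for the outcomes or a rule for declaring success.
- **What is compared.** Section 2.2 names two primary outcomes, 1RM and H:Q ratio, and says they will be compared across the three training groups. The primary analysis in section 4.1 is a repeated measures ANOVA of predicted against measured values. It names no between-group test. Section 2.3 describes the study as confirmatory.
- **Gender.** Section 2.2 states: "The sample size and population group are specified to allow the analysis of gender-specific differences on study results". Section 3.3 repeats this. At the end of the paragraph on validating HMF, section 4.1 adds: "The data from female and male participants will be analysed combined, as well as independently as two different groups".

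**The concern.** The sponsor recognised that three groups call for a stricter alpha and sized on one, yet the analysis section sets a different level for every test. Neither section deals with having two primary outcomes. A reader of the results could not tell which threshold a confirmatory claim had to meet, and the threshold and contrasts could be settled after the data are seen.

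The gender statement has a similar gap. The only sample size calculation has no sex term. If women and men are tested separately with 6 per group, a result that is significant in one sex and not in the other is likely to arise by chance and to be read as a sex difference, although that difference was never tested.

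**Working it through.** **1. The plan's own figure.** Inputs from section 3.1: d = 1.5, alpha 0.025, power 0.90, stated answer 11 per group. For two independent groups of n with SD 1, power is the probability that a noncentral t with 2n − 2 degrees of freedom and noncentrality d·√(n/2) exceeds the critical value.

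| n per group | one-sided 0.025 (= two-sided 0.05) | two-sided 0.025 |
|---|---|---|
| 10 | 0.887 | 0.809 |
| 11 | 0.917 | 0.853 |
| 12 | 0.939 | 0.889 |
| 13 | 0.956 | 0.916 |

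The t-test gives exactly 11 when 0.025 is one-sided and 13 when it is two-sided. The figure 11 does not settle which was meant. The normal approximation at two-sided 0.025 gives 2 × (2.241 + 1.282)² / 1.5² = 11.03, which rounds to 11 if not rounded up. A three-group ANOVA with f set to d/2 = 0.75 at 0.025 also gives 11.

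**2. What each reading implies.**
- One-sided 0.025: the levels in 3.1 and 4.1 agree numerically, but the allowance for three groups that 3.1 describes was never made.
- Two-sided 0.025: the allowance was made for sizing and then dropped in 4.1.

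Under both readings the two sections need reconciling.

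**3. Chance of any false positive in the between-group comparisons.** Section 4.1 does not say how groups are compared, so two methods are shown. Assumptions: no true effect, normal data, 3 groups of 12 (6 women, 6 men), correlation between the two outcomes from 0.8 to 0, and 40,000 simulated trials per setting (standard error at most 0.0025). *Overall F* means one ANOVA per outcome. *Pairwise* means three ungated t-tests per outcome.

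| Each test at 0.05 | Overall F | Pairwise |
|---|---|---|
| One outcome | 0.05 | 0.12 |
| Two outcomes | 0.08–0.10 | 0.18–0.23 |
| Two outcomes, plus women only and men only | 0.19–0.23 | 0.39–0.47 |

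For two outcomes with ungated pairwise tests at correlation 0.8, separate runs gave 0.18 to 0.19, so I quote about 19–23% for that cell. As a check, two independent outcomes by formula give 1 − 0.95² = 0.0975, in line with the upper F figure. At 0.025 per test, two outcomes give 0.04–0.05 with the overall F and 0.10–0.12 pairwise. The third row applies only if the by-sex sentence reaches 1RM and H:Q ratio.

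**4. What 6 per sex per group can show.**
- Within one sex, 6 against 6 at d = 1.5: power 0.65 at two-sided 0.05 and 0.51 at two-sided 0.025.
- For 90% power within a sex, 11 to 13 per group per sex would be needed, that is 6 × 11 = 66 to 6 × 13 = 78 participants against 36.
- Sex-by-group interaction: the difference between two groups in women minus the same difference in men uses four cell means of 6. Its standard error is √(4/6) = 0.816 SD, with 6 × 5 = 30 degrees of freedom. For 80% power at two-sided 0.05 it must be about 2.4 SD. An interaction of 1.5 SD has power 0.43.

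These 6-against-6 figures concern group comparisons. HMF against MRI is a within-person comparison in 6 women and 6 men, so they do not carry over to it.

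**The case against.** The strongest reply has five parts.

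- **The conflict may be one of notation.** One-sided 0.025 is two-sided 0.05, and the t-test then gives 11. This stands as a possible reading, but it leaves the three-group rationale in 3.1 without effect.
- **Section 4.1 names no pairwise tests.** This stands. A reader might infer that the plan carries a 47% chance of a false positive. The documents do not support that as the figure: it needs ungated pairwise tests, uncorrelated outcomes, and a by-sex sentence stretched from the HMF paragraph to the primary outcomes.
- **Three groups need not inflate error.** With exactly three groups, pairwise tests done only after a significant overall F keep the error for that outcome at its alpha. So it would be too strong to say that 0.025 cannot cover three contrasts; that holds for ungated tests. The plan states no such gate, however.
- **A stricter alpha can point the wrong way.** For predicted against measured values, the hypothesis in section 2.1 is accuracy, so a significant difference counts against it. Lowering alpha there would make a favourable finding of no significant difference easier to obtain. This stands and limits the fix.
- **Power for 1RM is not harmed.** A reader might infer that the mismatch leaves the trial underpowered. At two-sided 0.05, 12 per group have power 0.94 at d = 1.5. The issue is false positives and unsupported sex-specific inference.

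**Conclusion.** The point holds. The level used for sizing and the level set for analysis are not reconciled, sidedness is missing, and a study described as confirmatory has no rule for its two primary outcomes. At 0.05 per test, the chance of any false positive between-group result over both outcomes is about 8–10% with an overall ANOVA for each and about 19–23% with ungated pairwise tests. If the by-sex repeats also cover the primary outcomes, which the text leaves open, the ranges are about 19–23% and 39–47%. These figures assume that the group comparison in section 2.2 will be tested by one of those two methods.

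The claim that the sample size allows gender-specific analysis has no calculation behind it, and the numbers do not bear it out: power is 0.65 or 0.51 within a sex at d = 1.5, and an interaction must be about 2.4 SD to be found with 80% power. Separate analyses by sex also do not test whether the sexes differ. The power figures take d = 1.5 as given. It comes from a one-group change before and after training ("pre: $170.6 \pm 21.4$ kg, post: $200.8 \pm 19.0$ kg"), so they would be lower for a smaller difference between groups.

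**What to change.** Before any analysis:

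1. **Sections 3.1 and 4.1:** state the same alpha and its sidedness in both, and restate the power of 12 per group at that level.
2. **Section 4.1, between-group comparisons of change in 1RM and H:Q ratio:** name the test and control family-wise error at two-sided 0.05. Holm over the two outcomes is one valid choice among several, with pairwise contrasts either only after a significant overall test or in a fixed order. Say how alpha passes: the second outcome may be tested at 0.05 only when every confirmatory contrast of the first has been rejected; otherwise both stay at 0.025.
3. **Section 4.1, predicted against measured values:** do not apply the stricter alpha. Report the difference with a confidence interval.
4. **Section 4.1, sex:** replace separate significance tests in women and men with sex as a model term and a sex-by-group interaction estimate with confidence interval, labelled exploratory. Use sex-by-method for HMF against MRI.
5. **Sections 2.2 and 3.3:** delete the statement that the sample size was set for gender-specific differences.

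The cost is wording only, with no added participants or measurements. The downside is a stricter threshold for some between-group tests and a lower stated power: 0.889 for a single contrast at two-sided 0.025 and d = 1.5. If an overall F test at 0.025 is the gate and the largest group difference is 1.5 SD, power to pass it is 0.82 with the third group midway and 0.925 with two groups equal.
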